10.6 Appendix 6: Computation of SF-36v2[®] Score

The SF-36v2[®] will be scored for the 8 scales according to the standard SF-36v2[®] scoring algorithm (0-100 scale) explained in the SF-36v2[®] Japanese Manual (Fukuhara et al., 2011). The physical component score (PCS), mental component score (MCS), role/social component score (RCS) will be scored according to the standard SF-36v2[®] scoring algorithm (0-100 scale) explained in the same Manual. A higher score indicates a better health state. Prior to the analysis, the responses will be scored according to the following four steps.

1. Item recoding for the 10 items which require recoding
2. Computing raw scale scores by summing across items within the same scale (raw scale scores)
3. Transforming the raw scale scores into a 0-100 scale (transformed scale scores)
4. Normalizing the transformed scale scores with a mean of 50 and a standard deviation of 10 in the general Japanese population (norm-based scale scores)

Questions, coding and scoring of the 8 scales (Physical Functioning, Role-Physical, Bodily Pain, General Health, Vitality, Social Functioning, Role-Emotional, Metal Health), PCS and MCS are presented below.

Table 25.1. Physical Functioning: Verbatim Items and Scoring Information

Question Number	Verbatim Items
3.	The following questions are about activities you might do during a typical day. Does your health now limit you in these activities? If so, how much?
3a.	Vigorous activities , such as running, lifting heavy objects, participating in strenuous sports
3b.	Moderate activities , such as moving a table, pushing a vacuum cleaner, bowling, or playing golf
3c.	Lifting or carrying groceries
3d.	Climbing several flights of stairs
3e.	Climbing one flight of stairs
3f.	Bending, kneeling, or stooping
3g.	Walking more than a mile
3h.	Walking several hundred yards
3i.	Walking one hundred yards
3j.	Bathing or dressing yourself

Precoded and Final Values for Items 3a through 3j		
Response Choices	Precoded Item Value	Final Item Value
Yes, limited a lot	1	1
Yes, limited a little	2	2
No, not limited at all	3	3

Table 25.2. Role-Physical: Verbatim Items and Scoring Information

Question Number	Verbatim Items
4.	During the past 4 weeks, how much of the time have you had any of the following problems with your work or other regular daily activities as a result of your physical health?
4a.	Cut down the amount of time you spent on work or other activities
4b.	Accomplished less than you would like
4c.	Were limited in the kind of work or other activities
4d.	Had difficulty performing the work or other activities (for example, it took extra effort)

Precoded and Final Values for Items 4a through 4d		
Response Choices	Precoded Item Value	Final Item Value
All of the time	1	1
Most of the time	2	2
Some of the time	3	3
A little of the time	4	4
None of the time	5	5

Table 25.3. Bodily Pain: Verbatim Items and Scoring Information

Question Number	Verbatim Items
7.	How much bodily pain have you had during the past 4 weeks?
8.	During the past 4 weeks, how much did pain interfere with your normal work (including both work outside the home and housework)?

Precoded and Final Values for Item 7		
Response Choices	Precoded Item Value	Final Item Value
None	1	6.0
Very mild	2	5.4
Mild	3	4.2
Moderate	4	3.1
Severe	5	2.2
Very Severe	6	1.0

Scoring for Item 8 if both Items 7 and 8 are Answered			
Response Choices	If Item 8 Precoded Item Value	And Item 7 Precoded Item Value	Then Final Item Value
Not at all	1	1	6
	1	2 through 6	5
A little bit	2	1 through 6	4
Moderately	3	1 through 6	3
Quite a bit	4	1 through 6	2
Extremely	5	1 through 6	1

Scoring for Item 8 if Item 7 is Not Answered		
Response Choices	Precoded Item Value	Then Final Item Value
Not at all	1	6.0
A little bit	2	4.75
Moderately	3	3.5
Quite a bit	4	2.25
Extremely	5	1.0

Table 25.4. General Health: Verbatim Items and Scoring Information

Question Number	Verbatim Items
1.	In general, would you say your health is :
11.	How TRUE or FALSE is each of the following statements for you?
11a.	I seem to get sick a little easier than other people
11b.	I am as healthy as anybody I know
11c.	I expect my health to get worse
11d.	My health is excellent

Precoded and Final Values for Items 1 and 11a through 11d			
Item 1	Response Choices	Precoded Item Value	Final Item Value
	Excellent	1	5.0
	Very good	2	4.4
	Good	3	3.4
	Fair	4	2.0
	Poor	5	1.0
Items 11a and 11c	Response Choices	Precoded Item Value	Final Item Value
	Definitely True	1	1
	Mostly True	2	2
	Don't Know	3	3
	Mostly False	4	4
	Definitely False	5	5
Items 11b and 11d	Response Choices	Precoded Item Value	Final Item Value
	Definitely True	1	5
	Mostly True	2	4
	Don't Know	3	3
	Mostly False	4	2
	Definitely False	5	1

Table 25.5. Vitality: Verbatim Items and Scoring Information

Question Number	Verbatim Items
9.	These questions are about how you feel and how things have been with you during the past 4 weeks. For each question, please give the one answer that comes closest to the way you have been feeling. How much of the time during the past 4 weeks ...
9a.	Did you feel full of life?
9e.	Did you have a lot of energy?
9g.	Did you feel worn out?
9i.	Did you feel tired?

Precoded and Final Values for Items 9a, 9e, 9g and 9i			
Item 9a and 9e	Response Choices	Precoded Item Value	Final Item Value
	All of the time	1	5
	Most of the time	2	4
	Some of the time	3	3
	A little of the time	4	2
	None of the time	5	1
Items 9g and 9i	Response Choices	Precoded Item Value	Final Item Value
	All of the time	1	1
	Most of the time	2	2
	Some of the time	3	3
	A little of the time	4	4
	None of the time	5	5

Table 25.6. Social Functioning: Verbatim Items and Scoring Information

Question Number	Verbatim Items
6.	During the past 4 weeks, to what extent has your physical health or emotional problems interfered with your normal social activities with family, friends, neighbors, or groups?
10.	During the past 4 weeks, how much of the time has your physical health or emotional problems interfered with your social activities (like visiting with friends, relatives, etc.)?

Precoded and Final Values for Items 6 and 10			
Item 6	Response Choices	Precoded Item Value	Final Item Value
	Not at all	1	5
	Slightly	2	4
	Moderately	3	3
	Quite a bit	4	2
	Extremely	5	1
Item 10	Response Choices	Precoded Item Value	Final Item Value
	All of the time	1	1
	Most of the time	2	2
	Some of the time	3	3
	A little of the time	4	4
	None of the time	5	5

Table 25.7. Role-Emotional: Verbatim Items and Scoring Information

Question Number	Verbatim Items
5.	During the past 4 weeks, how much of the time have you had any of the following problems with your work or other regular daily activities as a result of any emotional problems (such as feeling depressed or anxious)?
5a.	Cut down on the amount of time you spent on work or other activities
5b.	Accomplished less than you would like
5c.	Did work or other activities less carefully than usual

Precoded and Final Values for Items 5a through 5c			
Item 5a through 5c	Response Choices	Precoded Item Value	Final Item Value
	All of the time	1	1
	Most of the time	2	2
	Some of the time	3	3
	A little of the time	4	4
	None of the time	5	5

Table 25.8. Mental Health: Verbatim Items and Scoring Information

Question Number	Verbatim Items
9.	These questions are about how you feel and how things have been with you during the past 4 weeks. For each question, please give the one answer that comes closest to the way you have been feeling. How much of the time during the past 4 weeks ...
9b.	Have you been very nervous?
9c.	Have you felt so down in the dumps that nothing could cheer you up?
9d.	Have you felt calm and peaceful?
9f.	Have you felt downhearted and depressed?
9h.	Have you been happy?

Precoded and Final Values for Items 9b, 9c, 9d, 9f and 9h			
Items 9b, 9c and 9f	Response Choices	Precoded Item Value	Final Item Value
	All of the time	1	1
	Most of the time	2	2
	Some of the time	3	3
	A little of the time	4	4
	None of the time	5	5
Item 9d and 9h	Response Choices	Precoded Item Value	Final Item Value
	All of the time	1	5
	Most of the time	2	4
	Some of the time	3	3
	A little of the time	4	2
	None of the time	5	1

Table 25.9. Reported Health Transition: Verbatim Items and Scoring Information

Question Number	Verbatim Items
2.	Compared to one year ago, how would you rate your health in general now?

Precoded and Final Values for Item 2			
Item 2	Response Choices	Precoded Item Value	Final Item Value
	Much better now than one year ago	1	1
	Somewhat better now than one year ago	2	2
	About the same as one year ago	3	3
	Somewhat worse now than one year ago	4	4
	Much worse now than one year ago	5	5

Use Table 25.10 to compute simple algebraic sums of the presented final item scores.

Table 25.10. Formulas for Scoring and Transforming Scales

SF-36v2 Scale	Sum Final Item Values (after recoding items as in Tables 7.1-7.9)	Lowest and Highest Possible Raw Scores	Possible Raw Score Range
Physical Functioning	3a + 3b + 3c + 3d + 3e + 3f + 3g + 3h + 3i + 3j	10, 30	20
Role-Physical	4a + 4b + 4c + 4d	4, 20	16
Bodily Pain	7 + 8	2, 12	10
General Health	1 + 11a + 11b + 11c + 11d	5, 25	20
Vitality	9a + 9e + 9g + 9i	4, 20	16
Social Functioning	6 + 10	2, 10	8
Role-Emotional	5a + 5b + 5c	3, 15	12
Mental Health	9b + 9c + 9d + 9f + 9h	5, 25	20

Formula for transformation of raw scale scores to 0-100 scale scores

$$\text{Transformed Scale} = \frac{(\text{Actual raw score} - \text{lowest possible raw score})}{(\text{Possible raw score range})} \times 100$$

After calculating the transformed scale score, the next step is to compute a z-score transformation. A z-score for each scale is computed by subtracting the 2007 General Japanese Population Means for each SF-36v2® scale and dividing the difference by the corresponding scale standard deviation (Table 20) from the 2007 General Japanese Population Means and Standard Deviations Used to Derive SF-36v2® Z-score. Formulas are listed below.

Table 25.11. 2007 General Japanese Population Means and Standard Deviations Used to Derive SF-36v2® Z-score

SF-36v2 Scale	Mean	Standard Deviation
Physical Functioning (PF)	89.13446	13.85045
Role-Physical (RP)	89.24007	18.80773
Bodily Pain (BP)	73.77098	22.39818
General Health (GH)	62.91007	18.76562
Vitality (VT)	62.82787	19.46255
Social Functioning (SF)	86.38347	19.40441
Role-Emotional (RE)	87.84637	20.01521
Mental Health (MH)	71.60598	18.62983

Step 1. Formulas for Z-score Standardization of SF-36v2® Scales

$$\begin{aligned}
 PF_Z &= (PF - 89.13446) / 13.85045 \\
 RP_Z &= (RP - 89.24007) / 18.80773 \\
 BP_Z &= (BP - 73.77098) / 22.39818 \\
 GH_Z &= (GH - 62.91007) / 18.76562 \\
 VT_Z &= (VT - 62.82787) / 19.46255 \\
 SF_Z &= (SF - 86.38347) / 19.40441 \\
 RE_Z &= (RE - 87.84637) / 20.01521 \\
 MH_Z &= (MH - 71.60598) / 18.62983
 \end{aligned}$$

Means and standard deviations are from Table 25.11.

Step 2. Norm-based Transformation of SF-36v2® Z-scores

The next step involves transforming each SF-36v2® z-score to the norm-based (50, 10) scoring. This is accomplished by multiplying each z-score from Step 1 by 10 and adding the resulting product to 50. Formulas are listed below.

$$\begin{aligned}
 \text{Norm-Based Physical Functioning (PF)} &= 50 + (PF_Z \times 10) \\
 \text{Norm-Based Role-Physical (RP)} &= 50 + (RP_Z \times 10) \\
 \text{Norm-Based Bodily Pain (BP)} &= 50 + (BP_Z \times 10) \\
 \text{Norm-Based General Health (GH)} &= 50 + (GH_Z \times 10) \\
 \text{Norm-Based Vitality (VT)} &= 50 + (VT_Z \times 10) \\
 \text{Norm-Based Social Functioning (SF)} &= 50 + (SF_Z \times 10) \\
 \text{Norm-Based Role-Emotional (RE)} &= 50 + (RE_Z \times 10) \\
 \text{Norm-Based Mental Health (MH)} &= 50 + (MH_Z \times 10)
 \end{aligned}$$

PCS, MCS and RCS are scored in three steps as explained below:

Step 1. Z-score Standardization of SF-36v2® Scales

The first consists of standardizing each of the 8 SF-36v2® scales using a z-score transformation. This is the same as Step 1 used in the norm-based scoring of the 8 SF-36 scales.

Step 2. Aggregating Scales in Estimating Aggregate Physical, Mental, and Role/social Component Scores

After a z-score has been computed for scale, the second step involves computation of aggregate scores for the physical, mental and role/social components using the physical and mental factor score coefficients from 2002 survey as given in Table 25.12.

Table 25.12. 2002 Factor Score Coefficients Used to Derive PCS, MCS, and RCS Scale Scores

SF-36v2 Scale	PCS	MCS	RCS
Physical Functioning (PF)	0.67908	-0.20472	-0.13048
Role Physical (RP)	0.22298	-0.27243	0.40393
Bodily Pain (BP)	0.37244	0.14644	-0.21786
General Health (GH)	0.36992	0.33933	-0.41710
Vitality (VT)	-0.08420	0.46413	-0.13120
Social Functioning (SF)	-0.30769	0.06727	0.49261
Role Emotional (RE)	-0.14256	-0.15597	0.61022
Mental Health (MH)	-0.33155	0.44572	0.10326

Computation of an aggregate physical component score consists of multiplying each SF-36v2[®] scale z-score by its respective physical factor score coefficient and summing the eight products, as shown below. Similarly, an aggregate mental, and role/social component score is obtained by multiplying each SF-36v2[®] scale z-score by its respective mental factor score coefficient and summing the eight products.

Formulas for Aggregating Scales in Estimating Aggregate Physical, Mental, and Role/social Component Scores (Standard Form)

$$\begin{aligned}
 \text{AGG_PHYS} &= (\text{PF_Z} \times 0.67908) + (\text{RP_Z} \times 0.22298) + (\text{BP_Z} \times 0.37244) + (\text{GH_Z} \times 0.36992) + \\
 &\quad (\text{VT_Z} \times -0.08420) + (\text{SF_Z} \times -0.30769) + (\text{RE_Z} \times -0.14256) + (\text{MH_Z} \times -0.33155) \\
 \text{AGG_MENT} &= (\text{PF_Z} \times -0.20472) + (\text{RP_Z} \times -0.27243) + (\text{BP_Z} \times 0.14644) + (\text{GH_Z} \times 0.33933) + \\
 &\quad (\text{VT_Z} \times 0.46413) + (\text{SF_Z} \times 0.06727) + (\text{RE_Z} \times -0.15597) + (\text{MH_Z} \times 0.44572) \\
 \text{AGG_ROLE} &= (\text{PF_Z} \times -0.13048) + (\text{RP_Z} \times 0.40393) + (\text{BP_Z} \times -0.21786) + (\text{GH_Z} \times -0.41710) + \\
 &\quad (\text{VT_Z} \times -0.13120) + (\text{SF_Z} \times 0.49261) + (\text{RE_Z} \times 0.61022) + (\text{MH_Z} \times 0.10326)
 \end{aligned}$$

Step 3. Formulas for T-score Transformation of Component Scores (Standard Form)

The third step involves transforming each component score to the norm-based (50, 10) scoring. This is accomplished by multiplying each aggregate component scale score by 10 and adding the resulting product to 50.

$$\begin{aligned}
 \text{Transformed Physical (PCS)} &= 50 + (\text{AGG_PHYS} \times 10) \\
 \text{Transformed Mental (MCS)} &= 50 + (\text{AGG_MENT} \times 10) \\
 \text{Transformed Mental (RCS)} &= 50 + (\text{AGG_ROLE} \times 10)
 \end{aligned}$$

Missing Data in an Individual Questionnaire

In the event that data is missing for an individual item from the scales of the SF-36v2[®] Health Status Survey, the average value of the completed items in the corresponding scale will be used as an estimate of the missing item. If more than 50 percent of the items from a scale are missing for an individual questionnaire, the corresponding deficient scale(s) will be excluded from analyses.

Items in each scale are given below:

SF-36v2 Scale	No. Items	Items	Minimum No. Non-Missing Items for Imputation of Missing Values
PF	10	3a, 3b, 3c, 3d, 3e, 3f, 3g, 3h, 3i, 3j	5
RP	4	4a, 4b, 4c, 4d	2
BP	2	7, 8	1
GH	5	1, 11a, 11b, 11c, 11d	3
VT	4	9a, 9e, 9g, 9i	2
SF	2	6, 10	1
RE	3	5a, 5b, 5c	2
MH	5	9b, 9c, 9d, 9f, 9h	3

Example Showing the Mechanics of Imputation Technique:

Suppose for a subject the items 1, 3b, 3e, 3f, 4a, 4b, 11b, 11d, 5a and 5b are missing. First group the missing items according to the scale:

- GH: Items 1, 11b, 11d
- PF: Items 3b, 3e, 3f
- RP: Items 4a and 4b
- RE: Items 5a and 5b

GH consists of 5 items and 3 are missing. That is only 2 have non-missing scores. Since at least half of the items are not non-missing, missing items 1, 11a and 11d cannot be imputed. Therefore for this subject, the General Health scale score will be missing.

PF consists of 10 items. So, for this subject 7 of the items are non-missing. That is, at least half of the items are non-missing. Therefore replace the missing Items 3b, 3e and 3f scores by the average score of the non-missing items, i.e., replace by $(3a + 3c + 3d + 3g + 3h + 3i + 3j) / 7$.

RP consists of 4 items and two are missing. So at least half are non-missing. Therefore replace the missing item scores 4a and 4b by $(4c+4d) / 2$.

RE consists of 3 and two are missing. That is, more than half of the item scores are missing. Therefore, missing scores 5a and 5b cannot be imputed for this subject and thus RE scale score for this subject will be missing.

10.7 Appendix 7: Computation of WPAI Scale Score

Work Productivity and Activity Impairment Questionnaire: WPAI

In this study, the following scoring methods are applied. These scoring methods are based on the specific health problem version of WPAI (WPAI:SHP).

Question Number	Contents
1.	1. Are you currently employed (working for pay)?
2.	2. During the past seven days, how many hours did you miss from work because of problems associated with your rheumatoid arthritis?
3.	3. During the past seven days, how many hours did you miss from work because of any other reason, such as vacation, holidays, time off to participate in this study?
4.	4. During the past seven days, how many hours did you actually work?
5.	5. During the past seven days, how much did your rheumatoid arthritis affect your productivity while you were working?
6.	6. During the past seven days, how much did your rheumatoid arthritis affect your ability to do your regular daily activities, other than work at a job?

Scores:

Multiply scores by 100 to express in percentages.

- Percent work time missed due to problem: $Q2/(Q2+Q4)$
- Percent impairment while working due to problem: $Q5/10$
- Percent overall work impairment due to problem:
 $Q2/(Q2+Q4)+[(1-(Q2/(Q2+Q4)))x(Q5/10)]$
- Percent activity impairment due to problem: $Q6/10$

10.8 Appendix 8: AE of Special Interest

1. Serious Infections
 - AE which belongs to SOC of Infections and infestations (10021881) and regarded as serious.
2. Malignancies

Following PT terms are included.

Diffuse large B-cell lymphoma (10012818), Bladder cancer (10005003), Breast cancer (10006187), Carcinoma in situ (10061450), Colon cancer (10009944), Gastric cancer (10017758), Renal cancer (10038389), Squamous cell carcinoma (10041823), Small cell lung cancer stage unspecified (10041071), Extraskelatal chondrosarcoma (10015838), Lymphoma (10025310), Thyroid cancer (10066474).
3. Herpes Zoster Related Disease (Herpes Zoster and Varicella)

Following PT terms are included.

Herpes zoster (10019974), Herpes zoster iridocyclitis (10019980), Herpes zoster ophthalmic (10019983), Herpes zoster multi-dermatomal (10058428), Herpes zoster infection neurological (10061208), Herpes zoster oticus (10063491), Herpes zoster disseminated (10065038), Encephalitis post varicella (10014603), Varicella (10046980), Varicella post vaccine (10063522).
4. Herpes Zoster

Following PT terms are included.

Herpes zoster (10019974), Herpes zoster iridocyclitis (10019980), Herpes zoster ophthalmic (10019983), Herpes zoster multi-dermatomal (10058428), Herpes zoster infection neurological (10061208), Herpes zoster oticus (10063491), Herpes zoster disseminated (10065038).
5. Varicella

Following PT terms are included.

Encephalitis post varicella (10014603), Varicella (10046980), Varicella post vaccine (10063522).
6. Infections That Require Intravenous Anti-infectious Therapy

All PTs which belong to SOC of Infections and Infestations (10021881) for which there is an intravenous concomitant medication (antibiotics, antivirals, antifungals, etc.) associated with that event for that patient.

10.9 Appendix 9: Standard Toxicity Grading for Laboratory Tests According to National Cancer Institute Common Terminology Criteria for Adverse Events (NCI-CTCAE) v4.0

Table 26. Standard Toxicity Grading for Laboratory Tests According to National Cancer Institute Common Terminology Criteria for Adverse Events (NCI-CTCAE) v4.0

Test Name	Test Code	Units ¹	Direction of Change / AE Term	CTCAE Grade ²					NCI Ref.		
				0	1	2	3	4	Version	Page	Units
Alanine Aminotransferase (ALT/SGPT)	ALT	n/a	Increase/ Alanine aminotransferase increased	WNL	>ULN - ≤ 3.0×ULN	>3.0×ULN - ≤ 5.0×ULN	>5.0×ULN - ≤ 20.0×ULN	>20.0×ULN	4.0	107	n/a
Albumin	ALB	g/dL	Decrease/ Hypoalbuminemia	WNL	≥3 - <LLN	≥2 - <3	<2		4.0	116	g/dL
Alkaline Phosphatase	ALP	n/a	Increase/ Alkaline phosphatase increased	WNL	>ULN - ≤ 2.5×ULN	>2.5×ULN - ≤ 5.0×ULN	>5.0×ULN - ≤ 20.0×ULN	>20.0×ULN	4.0	107	n/a
Amylase	AMY	n/a	Increase/ Serum amylase increased	WNL	>ULN - ≤ 1.5×ULN	>1.5×ULN - ≤ 2.0×ULN	>2.0×ULN - ≤ 5.0×ULN	>5.0×ULN	4.0	112	n/a
Aspartate Aminotransferase (AST/SGOT)	AST	n/a	Increase/ Aspartate aminotransferase increased	WNL	>ULN - ≤ 3.0×ULN	>3.0×ULN - ≤ 5.0×ULN	>5.0×ULN - ≤ 20.0×ULN	>20.0×ULN	4.0	107	n/a
Calcium Corrected ³	CACOR	mg/dL	Increase/ Hypercalcemia	WNL	>ULN - ≤ 11.5	>11.5 - ≤ 12.5	>12.5 - ≤ 13.5	>13.5	4.0	115	mg/dL
Calcium Corrected ³	CACOR	mg/dL	Decrease/ Hypocalcemia	WNL	≥8.0 - <LLN	≥7.0 - <8.0	≥6.0 - <7.0	<6.0	4.0	116	mg/dL
Total Cholesterol	TCHOL	mg/dL	Increase/ Cholesterol high	WNL	>ULN - ≤ 300	>300 - ≤ 400	>400 - ≤ 500	>500	4.0	109	mg/dL
Creatine Phosphokinase	CPK	n/a	Increase/ CPK increased	WNL	>ULN - ≤ 2.5×ULN	>2.5×ULN - ≤ 5×ULN	>5×ULN - ≤ 10×ULN	>10×ULN	4.0	109	n/a
Creatinine	CREAT	n/a	Increase/ Creatinine increased	WNL	>ULN - ≤ 1.5×ULN or >ULN - ≤ 1.5×baseline	>1.5×ULN - ≤ 3.0×ULN or >1.5×ULN - ≤ 3.0×baseline	>3.0×ULN - ≤ 6.0×ULN or >3.0×ULN - ≤ 3.0×baseline	>6.0×ULN	4.0	109	n/a
Estimated glomerular filtration rate	GFR	mL/min per 1.73 m ²	Decrease/ Chronic kidney disease	Not applicable⁸	Not applicable⁸	30 - 59	15 - 29	<15	4.0	147	mL/min per 1.73 m ²

Gamma Glutamyl Transferase (GGT)	GGT	n/a	Increase/ GGT increased	WNL	>ULN - ≤2.5×ULN	>2.5×ULN - ≤5.0×ULN	>5.0×ULN - ≤20.0×ULN	>20.0×ULN	4.0	110	n/a
Glucose	GLUC	mg/dL	Decrease/ Hypoglycemia	WNL	≥55 - <LLN	≥40 - <55	≥30- <40	<30	4.0	117	mg/dL
Hemoglobin	HGB	g/dL	Increase/ Hemoglobin increased	WNL	Increase in >0 - 2 g/dL above ULN or above baseline if baseline is above ULN	Increase in >2 - 4 g/dL above ULN or above baseline if baseline is above ULN	Increase in >4 g/dL above ULN or above baseline if baseline is above ULN		4.0	111	g/dL
Hemoglobin	HGB	g/dL	Decrease/ Anemia	WNL	≥10 - <LLN	≥8 - <10.0	<8		4.0	3	g/dL
Leukocytes (WBC)	WBC	10 ³ /μL	Decrease/ White blood cell decreased	WNL	≥3.0 - <LLN	≥2.0 - <3.0	≥1.0 - <2.0	<1.0	4.0	113	10 ³ /μL
Lymphocytes, Absolute Units	LYMP HAB	10 ³ /μL	Decrease/ Lymphocyte count decreased	Not applicable⁸	Not applicable⁸	≥0.5 - <0.8	≥0.2 - <0.5	<0.2	4.0	111	10 ³ /μL
Lymphocytes, Absolute Units	LYMP HAB	10 ³ /μL	Increase/ Lymphocyte count increased	Not applicable⁸		>4 - 20	>20		4.0	111	10 ³ /μL
Magnesium	MG	mg/dL	Increase/ Hypermagnesemia	WNL	>ULN - ≤3.0		>3.0 - ≤8.0	>8.0	4.0	115	mg/dL
Magnesium	MG	mg/dL	Decrease/ Hypomagnesemia	WNL	≥1.2 - <LLN	≥0.9 - <1.2	≥0.7 - <0.9	<0.7	4.0	117	mg/dL
Absolute Neutrophil Count	ANC	10 ³ /μL	Decrease/ Neutrophil count decreased	Not applicable⁸	Not applicable⁸	≥1.0 - <1.5	≥0.5 - <1.0	<0.5	4.0	112	10 ³ /μL
Phosphate (Phosphorus)	PHOS	mg/dL	Decrease/ Hypophosphatemia	WNL	Not applicable⁸	≥2.0 - <2.5	≥1.0 - <2.0	<1.0	4.0	117	mg/dL
Platelets	PLT	10 ³ /μL	Decrease/ Platelet count decreased	WNL	≥75.0 - <LLN	≥50.0 - <75.0	≥25.0 - <50.0	<25.0	4.0	112	10 ³ /μL
Potassium	K	mEQ/L	Increase/ Hyperkalemia	WNL	>ULN - ≤5.5	>5.5 - ≤6.0	>6.0 - ≤7.0	>7.0	4.0	115	mEQ/L ⁷
Potassium ⁴	K	mEQ/L	Decrease/ Hypokalemia	WNL		≥3.0 - <LLN	≥2.5 - <3.0	<2.5	4.0	117	mEQ/L ⁷
Urine Protein ⁵	UPROT		Increase/ Proteinuria	WNL	+	++	+++ or ++++		4.0	149	n/a
Sodium	NA	mEQ/L	Increase/ Hyponatremia	WNL	>ULN - ≤150	>150 - ≤155	>155 - ≤160	>160	4.0	116	mEQ/L ⁷

Sodium	NA	mEQ/L	Decrease/ Hyponatremia	WNL	≥130 - <LLN		≥120 - <130	<120	4.0	117	mEQ/L ⁷
Total Bilirubin	TBI LI	n/a	Increase/ Blood bilirubin increased	WNL	>ULN - ≤1.5×UL N	>1.5×U LN - ≤3.0×U LN	>3.0×U LN - ≤10.0× ULN	>10.0 ×ULN	4.0	107	n/a
Triglycerid es	TRI G	mg/dL	Increase/ Hypertriglyceri demia	WNL	> ULN ⁹ - ≤300	>300 - ≤500	>500 - ≤1000	>1000	4.0	116	mg/d L
Uric Acid ⁶	UAC ID	mg/dL	Increase/ Hyperuricemia	WNL			>ULN - 10	>10	4.0	116	mg/d L

¹ "n/a" is specified if the criteria are based strictly on a comparison of the value to its reference range.

² WNL = Within Normal Limits; LLN = Lower Limit of Normal; ULN = Upper Limit of Normal.

³ **Calcium Corrected** will be derived using the following formula: Calcium Corrected = $0.8 \times (4.0 - \text{Albumin}) + \text{Calcium}$, where 4.0 represents the average albumin level in g/dL, Albumin is measured in unit of g/dL, and Calcium is measured in unit of mg/dL.

⁴ Hypokalemia Grade 2 is the same as Grade1 but has additional clinical criteria that cannot be assessed. Therefore, it was decided to grade all criteria falling within $\geq 3.0 - < \text{LLN}$ as grade 2.

⁵ For Urine Protein, the maximum category is "++++", while NCI CTCAE version4.0 doesn't define "+++", "++++". So, these are defined as grade 3 per internal discussion.

⁶ Hyperuricemia Grade 3 is the same as Grade1 but has additional clinical criteria that cannot be assessed. Therefore, it was decided to grade all criteria falling within $> \text{ULN} - 10$ mg/dL as grade 3.

⁷ For hyperkalemia, hypokalemia, hypernatremia and hyponatremia, the unit in the NCI reference is mmol/L, which has been converted to mEQ/L by multiplying 1.

⁸ For ANC, LYMPHAB, GFR, there are no reference range in central laboratory, so, NCI CTCAE grading scale is only defined for not-related reference range category. For PHOS, LLN=2.5mg/dL, while NCI Grade 1 is defined " $\geq 2.5 - < \text{LLN}$ ", so Grade 1 can't be defined.

⁹ For TRIG, the upper limit of normal range is 149 mg/dL. Therefore, WNL for Grade 0 is up to 149 mg/dL. But the lower limit of Grade 1 is originally more than 150 mg/dL. So, the definition for the lower limit of grade 1 is changed from 150 mg/dL to ULN.

- Hyperuricemia (see pg. 116 of NCI document) cannot be assessed accurately without knowing whether or not the subject was experiencing physiologic consequences, so it is not included in the table.
- Hemoglobinuria (see pg. 148 of NCI document) cannot be assessed accurately without knowing clinical or diagnostic observations, so it is not included in the table.
- Troponin T (see pg. 109 of NCI document) cannot be assessed accurately without knowing manufacturer ranges, so it is not included in the table.

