3.4.1.1 Criteria for Suspension or Interruption of the Study Drug or Reference Drug

The investigator/sub-investigator will immediately suspend or interrupt the study drug or reference drug if any of the following becomes applicable during treatment with the study drug or reference drug:

1. Clinical laboratory tests yielded any of the following results:
 - Hemoglobin < 8.0 g/dL
 - Absolute neutrophil count < 500/ μ L
 - Absolute lymphocyte count < 500/ μ L
 - Platelet count < 50000/ μ L
 - Creatinine (serum) levels measured at 2 consecutive hospital visits: above 150% of the baseline level
 - CPK > 10 \times ULN
2. β -D-glucan > ULN [in case of Japan: \geq 11 pg/mL]
3. The subject requires a medication whose concomitant administration is prohibited in the protocol because of possible drug-drug interaction.
4. The subject is suspected to be pregnant.
5. The investigator/sub-investigator judged it appropriate in the interest of the subject to suspend or interrupt the study drug or reference drug.
6. The sponsor made a request to suspend or interrupt the study drug or reference drug out of safety concerns for the subject.

- CONFIDENTIAL -

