Hemoglobin (HGB)	≥ 8.0 to $< 10.0 \text{ g/dL}$ $< 8.0 \text{ g/dL}$	Lowest
Hemoglobin (HGB)	$\geq (\text{Baseline-2})$ to $< (\text{Baseline-1}) \text{ g/dL}$ $< (\text{Baseline-2}) \text{ g/dL}$	Lowest
Hemoglobin (HGB)	
 Mild to Moderate: decrease from baseline ≥ 1 to $\leq 2 \text{ g/dL}$, Severe: decrease from baseline > 2 to $< 3 \text{ g/dL}$ or absolute value > 7 and $< 8 \text{ g/dL}$, Potentially Life Threatening: decrease from baseline ≥ 3 or absolute value $\leq 7 \text{ g/dL}$ 	Lowest
Creatine Phosphokinase (CPK)	> 500 to $\leq 2,000 \text{ U/L}$ $> 2,000 \text{ U/L}$	Highest
Creatine Phosphokinase (CPK)	$> 5 \times \text{Baseline}$	Highest
Creatine Phosphokinase (CPK)	$> 2 \times \text{ULN}$ to $\leq 5 \times \text{ULN}$ $> 5 \times \text{ULN}$ to $\leq 10 \times \text{ULN}$ $> 10 \times \text{ULN}$	Highest

Select Laboratory Variable	Reference Range	Highest/Lowest
Creatinine	> 1.5 × Baseline to ≤ 3.0 × Baseline > 3.0 × Baseline	Highest
Absolute Neutrophil Count (ANC)	≥ 1,500 to < 2,000 / mm ³ ≥ 500 to < 1,500 / mm ³ < 500 / mm ³	Lowest
Lymphocytes	≥ 200 to < 500 /uL < 200 /uL	Lowest
Lymphocytes	≥ 1,500 to < 2,000 / mm ³ ≥ 500 to < 1,500 / mm ³ < 500 / mm ³	Lowest
Platelets	≥ 2 × 10 ⁴ to < 5 × 10 ⁴ /uL < 2 × 10 ⁴ /uL	Lowest
Platelets	> 600,000 /uL	Highest
ULN = Upper Limit Normal Each categories are mutually exclusive.		

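### In SAP Table 26 the baseline limbs of the creatinine grades start at multiples of ULN, so they add nobody when baseline is normal and make grades overlap when it is raised

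*SAP*

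**What the plan says.** SAP 7.5.2 has selected laboratory results graded by program and reported as a shift from baseline to the worst value, up to Week 12 and over the entire period. The limits are in SAP 10.9 Appendix 9, Table 26. For creatinine, Grade 0 is WNL, which the table's notes define ("WNL = Within Normal Limits"). The other cells are:

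- Grade 1: ">ULN - ≤ 1.5×ULN or >ULN - ≤ 1.5×baseline"
- Grade 2: ">1.5×ULN - ≤ 3.0×ULN or >1.5×ULN - ≤ 3.0×baseline"
- Grade 3: ">3.0×ULN - ≤ 6.0×ULN or >3.0×ULN - ≤ 3.0×baseline", in which the baseline limb is ">3.0×ULN - ≤ 3.0×baseline"
- Grade 4: above 6.0×ULN, with no baseline limb.

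Several footnotes to Table 26 explain adaptations in other rows; none covers creatinine. Footnote 1 keeps the n/a unit for rows that rest only on the reference range. Creatinine is marked n/a although its cells cite baseline.

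Two other places measure creatinine purely against baseline. SAP 7.5.2, Table 7, classifies each subject's highest value as "> 1.5 × Baseline to ≤ 3.0 × Baseline" or as above 3.0×baseline. Protocol 3.4.1.1 suspends or interrupts treatment on this condition: "Creatinine (serum) levels measured at 2 consecutive hospital visits: above 150% of the baseline level".

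**The concern.** An alternative limb that names baseline would be expected to pick up subjects whom the ULN limb misses. Here the lower limit of the alternative is the same ULN multiple as in the first limb, so a value must already be above that multiple of ULN before baseline matters at all. The pattern repeats in three consecutive cells, so a PDF reading error is unlikely.

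Creatinine is a parameter of interest for this drug. Protocol 1.3 reports higher creatinine and lower eGFR than placebo in the phase II RA trial 015K-CL-RAJ1. At stake is whether the planned toxicity shift table reflects sizeable rises in subjects who start low in the normal range, and whether each value has exactly one grade. As printed, whoever writes the grading program must settle the overlaps without guidance from the plan.

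**Working it through.** The plan states no figure to reproduce. The check is interval algebra on the printed limits.

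**Notation.** Everything is in multiples of ULN, because the documents give no creatinine reference range. Let b be baseline and x the on-treatment value, with ULN = 1. Values up to ULN are taken as Grade 0.

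| Grade | ULN limb | Baseline limb |
|---|---|---|
| 1 | 1 < x ≤ 1.5 | 1 < x ≤ 1.5b |
| 2 | 1.5 < x ≤ 3 | 1.5 < x ≤ 3b |
| 3 | 3 < x ≤ 6 | 3 < x ≤ 3b |
| 4 | x > 6 | none |

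**Step 1: baseline at or below ULN (b ≤ 1).**
- Grade 1: 1.5b ≤ 1.5, so the baseline limb lies inside the ULN limb.
- Grade 2: 3b ≤ 3, so again it lies inside.
- Grade 3: it needs 3 < x ≤ 3b ≤ 3, which is empty.

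A grid with b from 0.20 to 1.00 and x from 0.01 to 8.00, in steps of 0.01, has 81 × 800 = 64,800 pairs. The baseline limbs were met by 850, 3,825 and 0 pairs for Grades 1, 2 and 3. They added 0, 0 and 0 pairs to the ULN limbs.

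**Step 2: baseline above ULN (b > 1).** The baseline limbs reach upward into the next grade.
- b = 1.2, x = 1.7: the Grade 1 baseline limb runs to 1.5 × 1.2 = 1.8, so x meets Grade 1. It also meets Grade 2, because 1.5 < 1.7 ≤ 3.
- b = 1.5, x = 4: the Grade 2 baseline limb runs to 3 × 1.5 = 4.5, so x meets Grade 2. It also meets Grade 3, because 3 < 4 ≤ 6.
- The Grade 3 baseline limb adds to its ULN limb only if 3b > 6, that is b > 2. The added values are then above 6, which is already Grade 4.

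Every value that a baseline limb adds therefore already belongs to a higher grade through ULN. Under a highest-grade rule alone, the printed baseline limbs would never change a grade at any baseline. A tie rule removes the ambiguity but leaves the limbs without effect.

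**Step 3: rises that stay Grade 0.** A value above 150% of baseline and still within range needs 1.5b < x ≤ 1, which is possible whenever b < 1/1.5 = 0.67. The largest rise that stays Grade 0 is 1/b:

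| Baseline (×ULN) | Largest value still Grade 0, as % of baseline |
|---|---|
| 0.5 | 200% |
| 0.6 | 167% |
| 0.667 | 150% |

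Example: b = 0.5 and x = 0.95 gives 0.95/0.5 = 190% of baseline. This falls in Table 7's first class and is Grade 0 in Table 26. If two consecutive visits both give 0.95, the Protocol 3.4.1.1 condition is met while the worst grade is still 0. For b between 0.667 and 1, a rise just over 150% is Grade 1.

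**Step 4: effect of using Table 7's cuts as the baseline limbs** (Grade 2: 1.5b < x ≤ 3b; Grade 3: x > 3b; highest grade met).

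| b | x | x/b | Grade as printed | Grade with Table 7 cuts |
|---|---|---|---|---|
| 0.5 | 0.8 | 1.60 | 0 | 2 |
| 0.3 | 1.0 | 3.33 | 0 | 3 |
| 0.9 | 1.36 | 1.51 | 1 | 2 |
| 1.2 | 1.7 | 1.42 | 1 and 2 | 2 |

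**The case against.** The strongest reply is that nothing is lost. Table 7 already counts highest creatinine above 1.5× and above 3.0× baseline, up to Week 12 and over the entire period. SAP Appendix 4, Table 23, adds a by-visit shift table for the same classes, and change from baseline is summarised by visit. SAP 7.5.2 plans no hypothesis test on laboratory data, and adverse event severity is graded separately by the investigator. This stands. A reader might infer that relative creatinine rises would go unreported, and the documents do not support that: one descriptive table is affected.

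A reader might also infer that a single value such as 190% of baseline triggers suspension, or that suspension depends on Table 26. Neither is so. The protocol criterion needs two consecutive visits and does not refer to the toxicity grades.

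Intent is not stated either. The hemoglobin-increase row uses baseline only when it is above ULN, so keeping in-range values at Grade 0 could be a deliberate choice. That would explain Grade 0, but not a limb that is empty for every subject with a normal baseline, nor two grades for one value.

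Finally, overlap needs a baseline above ULN, and Protocol 3.3 excludes estimated GFR of 40 mL/min or less. Overlap may therefore be uncommon, but the documents give no frequency.

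**Conclusion.** The creatinine row of Table 26 is defective as printed. For baselines at or below ULN its baseline limbs do nothing; above ULN they give some values two grades with no rule to choose. A subject with baseline below 0.67×ULN can pass 150% of baseline, and if this persists at two consecutive visits meet the protocol's suspension criterion, while the shift table shows Grade 0.

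The damage is limited to that shift table; no efficacy result and no Table 7 count changes. The number of subjects affected cannot be estimated, because the documents give neither a creatinine reference range nor a baseline distribution. The 0.67×ULN limit is algebra, not a count. The conclusion rests only on the printed limits and on Grade 0 meaning a value within the normal range. The wording of the external grading scale was not used. No view is taken on which clinical threshold is right.

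**What to change.** In the creatinine row of Table 26:

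1. Replace the baseline limbs of Grades 2 and 3 with the SAP's own Table 7 cuts: Grade 2, above 1.5×baseline up to 3.0×baseline; Grade 3, above 3.0×baseline. The ULN limbs stay.
2. Keep Grade 1 as above ULN up to 1.5×ULN, without a baseline limb, unless the sponsor sets and justifies a lower bound relative to baseline.
3. State that Grade 0 applies only when no higher grade is met, and that the highest grade met by either limb is assigned.
4. Add a footnote describing the creatinine criteria, as is done for other adapted rows, and correct the n/a unit entry.

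Grade 1 should not be defined as any rise above baseline. Table 7 has no such class, and it would mostly grade noise. With no true change, exchangeable readings and no ties, the largest of k post-baseline values exceeds baseline with probability k/(k+1). That is 3/4 = 75% for the 3 scheduled visits to Week 12 and 13/14 = 93% for the 13 to Week 52.

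The cost is an edit to one table row and to the grading program. The downside is that some subjects whose values are within range move to Grade 2 or 3, which the footnote should make plain. No change to the suspension rule is proposed.
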